#### 10.2.2. **Index and Non-Index Lesions**

All measurable lesions, up to a maximum of five lesions per organ and ten lesions in total, should be identified as index lesions to be measured and recorded in the medical record at Screening. The index lesions should be representative of all involved organs. In addition, index lesions should be selected based on their size (lesions with the longest diameters), their suitability for accurate repeat assessment by imaging techniques, and how representative they are of the patient's tumor burden. At screening, a sum of the products of diameters (SPD) for all index lesions will be calculated and considered the baseline sum of the products of diameters. Response criteria to be followed are listed below. The baseline sum will be used as the reference point to determine the objective tumor response of the index lesions at tumor assessment.

Measurable lesions, other than index lesions, and all sites of non-measurable disease, will be identified as non-index lesions. Non-index lesions will be recorded in the medical record and should be evaluated at the same assessment time points as the index lesions. In subsequent assessments, non-index lesions will be recorded as "stable or decreased disease," "absent," or "progression."

#### 10.2.3. **Evaluation of Target Lesions**

**Complete Response:** Complete disappearance of all target lesions.

**Partial Response:** Decrease, relative to baseline, of 30% or greater in the sum of the diameters of the two largest perpendicular diameters.

**Stable Disease:** Does not meet criteria for complete or partial response, in the absence of progressive disease. Subject with PR or CR that is not confirmed after at least 6 weeks are scored as SD unless they have new primary lesions.

**Progressive Disease:** At least 20% increase in the sum of the products of all target lesions (taking as reference the smallest sum recorded at or following baseline) and/or the appearance of any new lesion(s). In addition to the relative increase of 20%, the sum must also demonstrate an absolute increase of at least 5 mm.

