### 10.2. Definition of Measurable/Non-Measurable or Index/Non-Index Lesions

#### 10.2.1. Measurable and Non-Measurable Lesions

**Measurable lesions** are lesions that can be accurately measured in two perpendicular diameters, with at least one diameter  $\geq$  10 mm and the other dimension  $\geq$  10 mm (10 mm x 10 mm for spiral CT). The area will be defined as the product of the largest diameter with its perpendicular. Skin lesions can be considered measurable.

**Non-measurable (evaluable) lesions** are all other lesions, including unidimensionally measurable disease and small lesions (lesions without at least one diameter  $\geq$  20 mm), and any of the following:

- Lesions occurring in a previously irradiated area (unless they are documented as new lesions since the completion of radiation therapy), bone lesions, leptomeningeal disease, ascites, pleural or pericardial effusion, lymphangitis cutis/pulmonitis, abdominal masses

that are not pathologically/cytologically confirmed and followed by imaging techniques and cystic lesions.

All measurable and non-measurable lesions should be measured at screening/baseline and at the defined tumor assessment time points (~ every 9 weeks  $\pm$  5 days for the first 18 months then every 12 weeks thereafter). Extra assessments may be performed, as clinically indicated, if there is a suspicion of progression.

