### 14.8.2. Definition of Index Lesions Response Using irRC

- **irComplete Response (irCR):** Complete disappearance of all index lesions. This category encompasses exactly the same subjects as “CR” by the mWHO criteria.
- **irPartial Response (irPR):** Decrease, relative to baseline, of 50% or greater in the sum of the products of the two largest perpendicular diameters of all index and all new measurable lesions (i.e., percentage change in tumor burden). Note: the appearance of new measurable lesions is factored into the overall tumor burden, but does not automatically qualify as progressive disease until the SPD increases by  $\geq 25\%$  when compared to SPD at nadir.
- **irStable Disease (irSD):** Does not meet criteria for irCR or irPR, in the absence of progressive disease.
- **irProgressive Disease (irPD):** At least 25% increase percentage change in tumor burden (i.e., taking sum of the products of all index lesions and any new lesions) when compared to SPD at nadir.

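### Section 10.2.3 puts target-lesion progression on an area scale with a 5 mm length condition and partial response on diameters, so the target-growth part of the primary event cannot be applied as written

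*Combined protocol and SAP*

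**What the plan says.** Section 10.2.3 defines target-lesion progressive disease (PD) as "At least 20% increase in the sum of the products of all target lesions", measured from the smallest sum recorded, or any new lesion. It adds that "the sum must also demonstrate an absolute increase of at least 5 mm". Partial response (PR), in the same section, is a fall of "30% or greater in the sum of the diameters of the two largest perpendicular diameters".

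Section 10.2.1 fixes what a product is: "The area will be defined as the product of the largest diameter with its perpendicular". Section 10.2.2 deals with index lesions, not target lesions. There "a sum of the products of diameters (SPD) for all index lesions will be calculated" as the baseline, and the reader is told that the response criteria come next; 10.2.3 follows directly. No section defines a target lesion.

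Section 10.1 makes RECIST v1.1 the main response measure and the basis for disease-status guidance, including stopping therapy. It says that the PD definition is adapted by the text that follows. Section 12.2.1 defines the PFS event as death or RECIST v1.1 progression, whichever is earlier. Section 12.3 takes response rate (RR) from RECIST v1.1.

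Appendix H gives the separate immune-related criteria (irRC). PR there is a fall "of 50% or greater in the sum of the products of the two largest perpendicular diameters", and PD is a 25% rise in the sum of products.

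**The concern.** A sum of products is in mm², so it cannot rise by 5 mm. An assessor has to change either the scale of the sum or the unit of the condition, and the plan does not say which. PR and PD in one section also sit on different scales. The PR clause names two diameters per lesion, so even a reader who moves PD to diameters must still decide whether one or two per lesion enter the sum.

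This is the only numerical PD threshold for target lesions outside irRC, and it feeds the primary endpoint. Sites apply it in an open-label single-arm study, with scans every 9 weeks. Six months (about 26 weeks) falls between the week-18 and week-27 scans, so a patient called PD at week 18 on one reading but not on the other can change 6-month status.

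**Working it through.** **1. The plan's own figure.** Inputs from Section 12.1: n = 30, null rate 0.20, alternative 0.39, one-sided 10%, binomial. Find the smallest r with P(X ≥ r | 30, 0.20) ≤ 0.10.
- P(X ≥ 9 | 0.20) = 0.129, too high.
- P(X ≥ 10 | 0.20) = 0.061, so r = 10.
- Power: P(X ≥ 10 | 0.39) = 0.793, which agrees with the stated 80%.

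**2. How far apart the scales are.** With equal growth in both axes, area changes as the square of diameter.
- +20% in products is √1.20 − 1 = +9.5% in diameter.
- +20% in diameter is 1.20² − 1 = +44% in area.
- PR at −30% in diameter is 1 − 0.70² = 51% less area.
- The literal PD rule is not the irRC area rule either: +25% in products is √1.25 − 1 = +11.8% in diameter.

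**3. The same scans under each reading** (hypothetical lesions, 20% threshold).

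| Lesions | Sum of products | Sum of longest diameters | Sum of two diameters per lesion |
|---|---|---|---|
| A: three 20 x 20 mm grow to 22 x 22 mm | 1200 to 1452 mm² (+21%): PD | 60 to 66 mm (+10%): not PD | 120 to 132 mm (+10%): not PD |
| B: one 80 x 80 mm stable, four 20 x 20 mm grow to 28 x 28 mm | 8000 to 9536 mm² (+19.2%): not PD | 160 to 192 mm (+20%): PD | 320 to 384 mm (+20%): PD |
| C: three 20 x 20 mm become 24 x 18 mm | 1200 to 1296 mm² (+8%): not PD | 60 to 72 mm (+20%): PD | 120 to 126 mm (+5%): not PD |

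Products: A, 3 × 20² = 1200 and 3 × 22² = 1452. B, 80² + 4 × 20² = 8000 and 80² + 4 × 28² = 6400 + 3136 = 9536. C, 3 × 24 × 18 = 1296. The longest-diameter sums rise by 6, 32 and 12 mm, so the 5 mm condition does not decide any of the three. A and B go in opposite directions. C shows that the choice of diameters matters by itself.

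**4. What the 5 mm condition can mean.** Read as 5 mm², it has almost no effect. The smallest measurable lesion is 10 × 10 = 100 mm², of which 20% is already 20 mm², and the condition matters only if the smallest sum is below 5 / 0.20 = 25 mm². Read as 5 mm on a sum of longest diameters beside the +20% area rule, with uniform growth, it binds whenever that sum is below 5 / 0.0954 ≈ 52 mm.

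**5. Effect at the decision boundary.** If all 30 patients are classified, 10 progression-free rejects the null and 9 does not. Each reclassified patient moves the observed rate by 1/30 = 3.3 percentage points.

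**6. Related wording.** Section 10.2.1 accepts a lesion of 10 x 10 mm as measurable, yet classes as non-measurable "small lesions (lesions without at least one diameter" of 20 mm or more. A definition of target lesions has to settle this. Example B uses lesions of at least 20 mm, so it does not depend on the answer.

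**The case against.** The best defence is that the area scale is meant. Section 10.2.2 sets up a sum-of-products baseline and points straight to the criteria in 10.2.3, and 10.1 announces an adaptation of PD. That pointer is real and supports the area reading. It does not rescue the rule: the 5 mm condition still has the wrong unit, PR is still on diameters, and 10.1 does not say that the adaptation is a move to areas.

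A second defence is that 12.2.1 names RECIST v1.1 without citing 10.2.3, and that the adaptation in 10.1 may mean only the confirmation rule in 10.3. That is possible, but 10.2.3 remains the only written target-lesion threshold outside irRC.

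A third is scope. Death, new lesions and unequivocal non-target progression do not depend on this rule, and any classification doubt at n = 30 can tip a boundary result. Both points stand and limit the claim.

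A reader might go further in three ways that the documents do not support:
- **The area rule calls PD early and so lowers PFS.** This holds for uniform growth (example A) but reverses in example B.
- **The wording is a copying slip from the irRC text, so diameters were plainly intended.** The 10.2.3 clause measures from the smallest sum and counts new lesions. The irRC clause in 14.8.5 measures from baseline and does not count a new lesion by itself as PD. How the text came about cannot be established.
- **The sample size or power is wrong.** The stated power reproduces.

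**Conclusion.** The concern holds in a limited form. The written rule for PD by target-lesion growth cannot be applied literally, and the readings open to an assessor give different answers on the same scans. The exposed events are those from target-lesion growth alone. How many patients that is, and in which direction 6-month PFS would move, cannot be derived from the documents; N and power are unaffected. The consequence that can be shown is at the boundary: one patient read differently between 9 and 10 of 30 changes the conclusion. That assumes all 30 are classified at 6 months and that the exact binomial test implied by Section 12.1 is used. The correction is needed because a primary-event rule must be applicable as written, not because a bias has been shown.

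A separate and secondary inconsistency affects irRC response only. Section 14.8.2 defines PD by "taking sum of the products of all index lesions and any new lesions) when compared to SPD at nadir", while 14.8.5 compares with baseline. With a baseline of 1200 mm², a nadir of 900 and a current value of 1200, the change is 1200/900 − 1 = +33% under the first and 0% under the second. It does not touch the primary endpoint.

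**What to change.** For the PFS and RR endpoint definitions (Sections 10.1, 10.2.3, 12.2.1 and 12.3):
- Put PR, PD and the 5 mm condition on one stated scale with matching units. A sum of target-lesion diameters fits the mm unit and the PR clause. The sum-of-products pointer in 10.2.2 conflicts with it and must be reconciled.
- State which diameter or diameters per lesion enter the sum.
- Define target lesions, say how they relate to index lesions, and settle the 10 mm and 20 mm wording in 10.2.1.
- Say in 10.1 what the PD adaptation consists of.
- Separately, reconcile the irRC reference point in 14.8.2 and 14.8.5.

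The passages on stopping treatment that rely on the same criteria (10.1 and 10.3) must be reconciled with the endpoint text; no stopping rule is proposed here.

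The cost is protocol wording. The largest diameter and its perpendicular are already needed to form the product, so no new scans or readers are required. The change should be settled before further endpoint reads. Section 4.9.2 lets imaging stop at documented progression or new anticancer treatment, so a later PD date under another reading cannot always be re-derived from the diameters on file.

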#### 10.2.4. Evaluation of Non-Target Lesions

**Complete Response:** Complete disappearance of all non-target lesions and normalization of tumor marker level. All lymph nodes must be non-pathological in size (< 10 mm in short axis).

**Non-CR/Non-PD:** Persistence of one or more non-target lesion(s) and/or maintenance of tumor marker level above the normal limits.

**Progressive Disease:** Appearance of one or more new lesions and/or *unequivocal progression* of existing non-target lesions.

#### 10.3. Assessment of Disease According to RECIST v1.1 and irRC for Solid Tumors

If imaging shows PD, tumor assessment should be repeated  $\geq 4$  weeks later to confirm PD with the option of continuing treatment for clinically stable subjects. Clinically stable is defined by the following criteria:

- Absence of signs and symptoms indicating disease progression
- No decline in ECOG performance status
- Absence of rapid progression of disease

Absence of progressive tumor at critical anatomical sites (e.g., cord compression) requiring urgent alternative medical intervention.

	Clinically Stable		Clinically Unstable	
	Imaging	Treatment	Imaging	Treatment
First radiologic evidence of PD	Repeat imaging at $\geq 4$ weeks to confirm PD	May continue study treatment at the investigator's discretion while awaiting confirmatory scan	Repeat imaging at $\geq 4$ weeks to confirm PD if possible	Discontinue treatment
Repeat scan confirms PD	No additional imaging required	Discontinue treatment	No additional imaging required	N/A
Repeat scan shows SD, PR, or CR	Continue regularly scheduled imaging assessments every 9 weeks	Continue study treatment at the investigator's discretion	Continue regularly scheduled imaging assessments every 9 weeks	May restart study treatment if condition has improved and/or clinically stable per investigator's discretion

**Table 7: Imaging and Treatment after First Radiographic Evidence of Progression**

In determining whether the tumor burden has increased or decreased, investigators should consider all target lesions as well as non-target lesions. Subjects who are deemed clinically unstable are not required to have repeat imaging for confirmation. If radiologic progression is confirmed, then the subject will be discontinued from study treatment as specified in the protocol, and the first radiographic evidence of PD should be the date of progression. If radiologic progression is not confirmed, then the subject should resume/continue study treatment and have their next scan according to the Protocol-specified schedule. If progression is not confirmed and the subject continues on treatment, the next scan that documents disease progression (and is confirmed by a second scan at least 4 weeks later), will be considered the date of disease progression.

*Note:* If a subject with confirmed radiographic progression (i.e., 2 scans at least 28 days apart demonstrating progressive disease) is clinically stable or clinically improved, and there is no further increase in the tumor dimensions at the confirmatory scan, an exception may be considered to continue treatment if in the best interest of the patient clinically. Meaning, the investigator can continue if the risk-benefit is acceptable to continue the patient on study. Clinically stable subjects should also have at the confirmatory scan no further increase in the

target lesions, no unequivocal increase in non-target lesions, and no additional new lesions develop (non-worsening PD) to continue study treatment.

Imaging during the follow-up period is to be repeated every 9 weeks ( $63 \pm 5$  days) for subjects who discontinue study treatment for reasons other than disease progression until the subject experiences confirmed disease progression or starts a new antineoplastic therapy.

#### 10.4. Response Endpoints

Pembrolizumab and epacadostat are expected to trigger immune-mediated responses, which require activation of the immune system prior to the observation of clinical response. Such immune activation may take weeks to months to be evident.

**Table 8: Response Evaluations based on Endpoints**

	Progression Free Survival (PFS)	Response Rate (RR)	Overall Survival (OS)	Safety
Primary or Secondary	Primary	Secondary	Secondary	Secondary
Definition and Time Frame	Time from first treatment to documented disease progression or death due to any cause	Defined as proportion of patients with RECIST v1.1 response (sum of partial and complete responses).	Time from first treatment until the day of death due to any cause	Assessed on the basis of adverse events (AEs; graded according to the National Cancer Institute Common Terminology Criteria for Adverse Events, version 4.03)
Safety Issue (Yes/No)	No	No	No	Yes
Relevant Subset	Patients who receive baseline imaging and at least first follow-up imaging at 9 weeks.	Patients who receive baseline imaging and at least first follow-up imaging at 9 weeks.	All enrolled patients	Patients who receive at least 1 dose of pembrolizumab.
Measurement Method	CT or MRI every 9 weeks	CT or MRI every 9 weeks	CT or MRI every 9 weeks	CTCAE v5
Measurement Time Points	Every 9 weeks	Every 9 weeks	Every 9 weeks	Day 1 of each cycle

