6 Imaging on-study will be performed every 9 weeks (± 5 days) after the first dose of study treatment for the first 18 months then every 12 weeks thereafter. On-study imaging should follow calendar days and not be adjusted for delays in cycle starts or extension of treatment cycles due to toxicity. The same imaging technique should be used in a subject throughout the study.

7 Per the RECIST v1.1 and irRC, if imaging shows progressive disease, the imaging assessment should be performed at a minimum of 4 weeks later to confirm progression as described.

8 For patients that discontinue treatment for reasons other than disease progression, every effort should be made to continue monitoring their disease status by radiographic imaging at the imaging interval that was used at the time they came off study until 1) start of new anti-cancer therapy, 2) documented disease progression, 3) death, or 4) end of study, whichever occurs first.

9 If a prior scan was obtained within 4 weeks before the date of discontinuation, then a scan at the discontinuation visit is not required. In subjects who discontinue study drug without confirmed disease progression, a radiological evaluation should be repeated at the time of treatment discontinuation (i.e., date of discontinuation ± 4 week window).

10 If labs at screening are collected within 7 days of Cycle 1 Day 1, these do not need to be repeated at this visit.

11 Pre-dose laboratory results need to be within 2 days of dosing at all cycles.

12 See Table 2 for complete listing of all required laboratory tests required.

	Screening	Treatment Phase 				EOT	Post-Treatment	
		C1D1	C2D1	C3D1	Day 1 All Subsequent Cycles	Discontinuation Visit	Follow-Up Visits	Survival Follow-Up
Evaluation/Window	Day -28 to Day -1	Day 1	± 3 Days	± 3 Days	± 3 Days	+ 5 Days	Every 9 Weeks After Discontinuation (± 7 Days)	Every 12 Weeks (± 7 Days)
Hematology with differential	X	X	X	X	X	X	X	
Lipid panel	X	X	X	X	X	X		
Coagulation panel (PT, aPTT, INR) 	X							
Endocrine function testing 	X	X	X	X	X		X	
Serum pregnancy test or urine 	X							
Tumor Markers 		X	X	X	X	X		
Urinalysis	X	X	X	X	X	X		
Required research samples (blood)		X 	X	X	X			
TUMOR BIOPSY/ARCHIVAL TISSUE COLLECTION								
Fresh tissue collection for Correlative studies (tissue) 	X			X				

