## 12. STATISTICS CONSIDERATIONS

### 12.1. Statistical Design

This is a single-stage study for the doublet epacadostat and pembrolizumab. A 6-month PFS of 20% was observed using single agent pembrolizumab and is the basis for the null hypothesis of the present study (Bang, abstract 4001, GI ASCO 2015). We will enroll 30 patients over 18 months and follow patients for at least 6 months. This design has 80% power to reject a 20% PFS rate, if the true PFS is 39%. Calculation based on binomial probabilities with a one-sided significance of 10%. The level of significance for the primary endpoint in Phase 2 is one-sided 10%, which is deemed acceptable for a proof-of-concept study.

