## 12.2. Safety Analyses

### 12.2.1. Analysis Plan

The analysis will be done on the intent to treat population and patients who drop out will be censored at the point of last follow up.

The primary endpoint of the study is 6-month Progression-free survival (PFS), which is defined as number of days from the first day of taking study dose to the earlier of death or disease progression by RECIST v1.1 for solid tumors. Median PFS will be estimated using the Kaplan-Meier method.

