### 12.3. Secondary Analyses

Secondary efficacy analysis will be conducted for the efficacy evaluable population. Secondary endpoints and analyses are as follows:

To evaluate response rate (RR). Response will be determined by RECIST v1.1 for solid tumors. The 95% exact CI for the RR will be estimated using the Clopper-Pearson method. For objective responders, the duration of response is the time from the first objective response contributing to an objective response, to the first objective response of PD (by RECIST v1.1) occurring after the first objective response contributing to the objective response.

To evaluate overall survival (OS). Time-to-event data will be analyzed by the Kaplan-Meier method, treating subjects with no observed death or progression as censored at their last date known to be alive. For the OS analysis, the nonparametric Kaplan-Meier method will be used to estimate the survival time distribution and the median survival.

To assess the safety and tolerability of epacadostat in combination with pembrolizumab. AEs will be coded by the MedDRA, and incidences will be tabulated by preferred term and system organ class for all events, related events, and events  $\geq$  Grade 3. Severity of AEs will be based on the CTCAE v5 scale as indicated. Quantitative safety variables and their changes from baseline (laboratory, vital signs) will be summarized with descriptive statistics. Clinically significant abnormal values will be flagged and tabulated based on predefined criteria. Exposure will be analyzed by describing dose intensity, which is defined as the dose-received divided by the dose planned over a given time interval. This will be done by cycle as well as overall cycles received for epacadostat and pembrolizumab. For each cycle, incidences of dose reductions and cycle

delays will also be tabulated, by reason for the reduction or delay. The percentage of subjects with any delay and/or reduction will also be calculated.

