#### 12.4. **Sample Size**

We will enroll 30 patients over 18 months and follow patients for at least 6 months.

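### The Table 8 subset for response rate drops treated patients who die or deteriorate before any follow-up scan, and the population named in 12.3 is undefined, so the reported RR would be biased upward

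*Combined protocol and SAP*

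**What the plan says.** The response-rate population is addressed in section 10.4 (Table 8) and section 12.

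- **Table 8, RR column, definition row:** "Defined as proportion of patients with RECIST v1.1 response (sum of partial and complete responses"), with no qualifier on which patients.
- **Table 8, RR column, Relevant Subset row:** "Patients who receive baseline imaging and at least first follow-up imaging at 9 weeks".
- **Section 12.3:** "Secondary efficacy analysis will be conducted for the efficacy evaluable population". RR is the first endpoint listed under that sentence, with a 95% Clopper-Pearson interval. The population is not defined there or anywhere else.
- **Section 12.2.1:** "The analysis will be done on the intent to treat population". The text that follows concerns progression-free survival (PFS), not RR.

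No section says how a treated patient without a 9-week scan counts for RR. Section 4.9.2 allows scans earlier than the 9-weekly schedule when clinically indicated, and ends scheduled imaging at documented progression. Footnote 9 of the Schedule of Events adds that, for patients stopping without confirmed progression, "a radiological evaluation should be repeated at the time of treatment discontinuation".

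**The concern.** Membership of the Table 8 subset depends on something that happens after treatment starts, namely reaching a follow-up scan. A patient who dies at week 4, or becomes too ill to be scanned and never is, has been treated and has not responded. An all-treated denominator counts that patient as a failure, whereas the Table 8 subset removes the patient altogether. The patients removed are almost all non-responders, so the numerator stays put while the denominator shrinks.

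The trial has no control arm, and the readers most interested in RR will set it beside single-agent results. A few points gained through the denominator could be read as a contribution from epacadostat. Because the population in 12.3 is undefined, two analysts could also report different denominators from the same data, each claiming to follow the plan.

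**Working it through.** **The plan's own figure.** The only operating characteristic stated is for the primary endpoint: N = 30, null 20%, alternative 39%, one-sided 10%, 80% power (12.1). By exact binomial, requiring at least 10 of 30 gives a type I error of 0.061 and power of 0.793, which matches. Requiring at least 9 gives a type I error of 0.129, above 10%. This confirms N = 30 as the base. The plan gives no expected RR, target RR or interval width, so there is no RR figure to reproduce.

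**Inputs.**
- N = 30 (12.4: "We will enroll 30 patients over 18 months and follow patients for at least 6 months").
- 6-month survival of 66% and median survival of 11.4 months in the cited pembrolizumab gastric cohort (2.1).
- First scheduled scan at 9 weeks = day 63.
- An illustrative all-treated RR of 22%, or about 7 of 30 (0.22 × 30 = 6.6). It only sets a plausible responder count.

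**Step 1: inflation factor.** Let x be the responders and k the treated non-responders removed. The all-treated RR is x/30 and the subset RR is x/(30-k). Their ratio is 30/(30-k), whatever x is. This assumes that no responder is removed. A patient who missed the week-9 scan and responded later would be an exception, but should be rare.

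**Step 2: deaths before the first scheduled scan, constant hazard.**
- From 66% at 6 months (182.6 days): 1 - 0.66^(63/182.6) = 0.134, and 0.134 × 30 = 4.0 patients.
- From the median of 11.4 months (63 days = 2.07 months): 1 - 0.5^(2.07/11.4) = 0.118, or 3.5 patients.

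**Step 3: effect on RR.** With 13.4% removed, 0.22/(1 - 0.134) = 0.254, a rise of 3.4 points. The standard error at 22% and n = 30 is sqrt(0.22 × 0.78/30) = 0.0756, so the shift is 3.4/7.56 = 0.45 standard errors.

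**Step 4: effect on the exact interval, 7 responders.**

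| k | RR | 95% Clopper-Pearson |
|---|---|---|
| 0 | 7/30 = 23.3% | 9.9 to 42.3 |
| 3 | 7/27 = 25.9% | 11.1 to 46.3 |
| 4 | 7/26 = 26.9% | 11.6 to 47.8 |
| 6 | 7/24 = 29.2% | 12.6 to 51.1 |

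Both limits rise, though not by exactly the factor 30/(30-k), which applies to the point estimate. The interval also widens, from 32.4 points at k = 0 to 36.2 at k = 4. The k = 4 row corresponds to step 2. The k = 6 row is an assumption shown for scale.

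**Step 5: is the cited 22% an all-treated rate?** Section 2.1 gives a cohort of 39, with 22% partial response and 14% stable disease. No count out of 39 rounds to 22% (8/39 = 20.5%, 9/39 = 23.1%) or to 14% (5/39 = 12.8%, 6/39 = 15.4%). Among denominators from 25 to 39, only 36 (8/36 = 22.2%, 5/36 = 13.9%) and 37 (8/37 = 21.6%, 5/37 = 13.5%) fit both.

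**The case against.** **Is RR defined in three conflicting ways?** A reader might infer this, but the documents do not support it. The definition and subset rows of Table 8 can be read as one specification, the measure and its population. The efficacy-evaluable label in 12.3 may simply mean that subset. The intent-to-treat sentence in 12.2.1 leads into PFS, and 12.3 names a different population for secondary efficacy. For RR there is one explicit subset and one undefined label.

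**Are all documented early progressors removed?** A reader might infer this too. It follows only if the 9-week wording is read literally, since an earlier unscheduled scan could be taken as the first follow-up imaging. Table 7 and footnote 7 also ask for a repeat scan at least 4 weeks after first progression, so a patient with progression at week 5 may be rescanned at week 9 or later, although section 10.3 does not require this of clinically unstable patients. Footnote 9 supplies a scan for many who stop without confirmed progression. What stands is that the wording is ambiguous and could remove some patients whose progression was seen only on an earlier scan. The secure group is those with no follow-up scan at all.

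**Is the inflation large?** It is tempting to assume that 20% or 30% are removed. The documents give no such figure, and entry requires ECOG 0 or 1 and a life expectancy of at least 12 weeks. Only the 12 to 13% death estimate comes from the cited cohort, and that rests on a constant hazard.

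**Is the subset RR simply inflated against the 22% benchmark?** Step 5 suggests that the benchmark already rests on 36 or 37 of 39 patients, so part of the inflation would be shared. It should not be treated as an all-treated rate.

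**Does it matter?** RR has no hypothesis, threshold or decision rule, and does not affect N or power. That limits the consequence without removing the bias.

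**Conclusion.** The concern holds in this limited form. Followed as written, the Table 8 subset removes treated patients who cannot be responders, and 12.3 neither confirms nor corrects this because its population is undefined. The bias runs upward by 30/(30-k) in the point estimate, and both exact limits rise with it.

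The best-supported size is about 4 of 30 removed: 22% becomes about 25.4%, or with 7 responders 23.3% becomes 26.9%. This rests on a constant hazard from the cited cohort's 66% six-month survival, on this trial's patients having similar early mortality, and on every excluded patient being a non-responder. Larger values of k are assumptions, and with k = 0 there is no bias. The shift is under half a standard error in a descriptive secondary endpoint. It should be corrected, but it does not threaten the design.

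**What to change.** 1. In Table 8 (RR, Relevant Subset) and in 12.3, set the RR denominator to all patients who receive at least one dose of study treatment.
2. State that early death, progression before week 9, or no post-baseline scan counts as non-response.
3. Compute the Clopper-Pearson interval on that denominator.
4. Define the efficacy-evaluable population or delete the term.
5. Keep the scan-based subset as a labelled sensitivity analysis. This also allows comparison with published rates based on evaluable patients, as the 22% appears to be.

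The cost is a few lines of text in Table 8 and 12.3 and no new data. The downside is a slightly lower reported RR.
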